Home Pulmonary Rehabilitation for COPD

NCT03480386

August 23, 2021

General Study Information

Principal Investigator: [name]

Study Title: Home Pulmonary Rehabilitation for COPD

Protocol version number and date: Protocol Version9, August 23, 2021

Research Question and Aims

Hypothesis:

Home-based pulmonary rehabilitation with proper self-management support through health coaching rooted in motivational intervention during pulmonary rehabilitation will improve physical wellbeing, quality of life, increase daily physical activity, and decrease health care utilization for patients with COPD.

Aims, purpose, or objectives:

The ideal system for a home PR program requires straightforward, accurate technology to monitor physiological parameters, patient engagement, and simple exercises to be performed at home, all ensuring participant safety. Feedback is critical: MI-based health coaching, proven effective in COPD,⁶ can translate to higher self-efficacy, subsequently promoting better SM and improved QOL.^{15, 16}

The **aims** of this project:

- Home-based PR will increase PR uptake and adherence, a significant existing gap in COPD care.
- The addition of formal SM support through health coaching during PR may promote behavioral change to prolong the effects of PR on critical COPD health outcomes.
- The home-based PR program may meaningfully engage participants in successful SM and translate into sustained improved physical wellbeing (QOL), increased daily PA, and decreased health care utilization for patients with COPD.
- The proposed home-based PR system using “off-the-shelf” hardware and a previously commercialized software (accomplished through our Small Business Innovation Research Grant, SBIR 5R44HL114162-03) will have a high likelihood of implementation and dissemination once proven effective.

Background:

Role of Pulmonary Rehabilitation in Chronic Obstructive Pulmonary Disease care

International guidelines for managing Chronic Obstructive Pulmonary Disease (COPD), one of the main causes of morbidity and mortality worldwide,¹ suggest that pulmonary rehabilitation (PR) programs and self-management support (SM) are a critical part of treatment. A compelling body of evidence confirms that PR programs deliver improved exercise capacity, reduced breathlessness, and improved health-related quality of life (QOL)² and are associated with fewer acute exacerbations and hospital admissions—the biggest costs burden in health care.^{2, 7}

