In our previous work, we developed and tested (R01 HL09468), an effective program for SM in COPD through health coaching¹³ rooted in motivational interviewing (MI)^{13,14} that decreased COPD re-hospitalizations⁶ and produced a sustained improved QOL at six and 12 months.

Theoretical Framework

The theoretical framework of the proposed intervention (Fig. 1) is based on two guiding theories: self-efficacy theory^{15,17} and MI theory.¹⁶ In brief, training in MI prepares the health coach to initiate conversations in the spirit of MI (compassion, acceptance, evocation of the client's values, and collaboration) and skills (open questions, a non-coercive approach for change, and making the participant the expert and final decision-maker). The latter (spirit and skills) may not only impact social persuasion (part of self-efficacy theory) but also directly increase self-efficacy (confidence) that leads to higher SM abilities (behavior change). Pulmonary rehabilitation directly impacts the foundations of the self-efficacy theory: mastery in PA, by engaging in daily exercises (Aim 3, measured by activity monitor), social persuasion (weekly feedback from a trustworthy coach) and emotions and physiology (exercise is a known positive factor impacting emotions and COPD physiology). Self-efficacy (Sub aim 2 measured by CRQ Mastery) translates into SM or behavior change (Aim 2 measured by SMAS30) which in turn impacts physical QOL (Aim 1). We have recently confirmed and published the independent relationship between MI health coaching, SM and quality of life.^{6,18,19} A proposed path analysis will confirm the proposed framework.

*Compassion, Acceptance, Evocation, Collaboration; †Open-ended questions, affirmations, reflective listening, and summaries

Fig. 1. Theoretical framework.

Innovation

The project is truly innovative due to the purely home-based nature of the system, the simplicity and accuracy of data collection attained with using commercially available monitors, and the addition of health coaching to engage and provide weekly feedback to participants. Previous studies required participants in home-based training groups to attend SM education^{4,20} or weekly monitoring in the clinic or hospital.²¹ These approaches fail to overcome the transportation and mobility-related barriers to attendance, perpetuating the present lack of adherence.

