About right	78%
Too much	0%
Frequency of calls at end of study (%)	
Too little	43%
About right	57%
Too much	0%
Recommend to others (%)	
Yes	96%

Fig. 7. Qualitative feedback of health coaching

based
Health that
A

Randomized Study:

Participants will be randomly assigned in equal proportion to one of two treatments: home PR with health coaching or the attention waitlist control (Fig. 9). Participants randomly assigned to the intervention will receive three months of home PR followed by six months of usual care.

Participants randomly assigned to the active control group will receive three months of usual care plus educational materials and non-coaching calls (matching the number of contacts in the intervention group), followed by three months of home PR plus health coaching and three months of usual care.

Phase 2: Participants randomized to intervention will not change; three months of home PR followed by six months of usual care. Participants enrolled in the active control group will follow the scheme listed above; 3 months of usual care followed by three months of home PR and three months of usual care. During the control wait period they will receive a pamphlet of 12 Healthy Habits during the enrollment period as well as two letters during the control period. The letters will remind them to review the 12 Healthy Habits and will remind them that the exercise portion of the study will start soon.

Phase 3: Forty Mayo participants who have completed the intervention (the 12 weeks of home-based pulmonary rehab with health coaching) will be randomly selected to complete a qualitative interview to explore areas related to the intervention, quality of life and symptom severity. The purpose of the qualitative interview is to take an in-depth look at the appropriateness of the intervention as a potential method of treatment as well as examining the impact on the participant as a whole. Mayo Clinic participants who have completed the intervention portion of the study will be contacted via the telephone to inquire about their interest in participating in the interview. If interested, oral consent will be conducted. A mutually agreed upon time and date for the interview will be confirmed. (A phone script will be used.) The participants will receive \$40 for consideration of their time.

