All calls will be recorded to ensure compliance with the protocol and MI principles (10% of all calls will be reviewed). Recorded files are saved on the restricted research drive, accessible only to study staff. The recorded files are to be deleted off the drive after analysis of the intervention is completed and study is finished. Only ten percent of the calls are reviewed, and that is to feedback and training to the health coach.

Coach Training

Details of the health coach training have been published and publicly available.¹³ In brief, the health coach intervention is purposefully designed to be delivered by PR professionals, respiratory therapists, or nurses, the most common providers of care in PR, as opposed to psychologists. Training includes: 1) face-to-face education on theory and strategies associated with SM education and MI in general (six hours); 2) reading materials detailing skills and strategies associated with SM education and MI; 3) role play-based experiential learning of intervention strategies with participant vignettes (five hours); and 4) recorded and reviewed intervention sessions in which interventionists provide tailored training to discuss strengths, missed opportunities for use of intervention strategies, and any deviations from the intervention protocol (10 hours over six months). The rationale for the latter is that training sessions that incorporate feedback from coded sessions increase skill retention. All training sessions will be audio or video recorded for future review to minimize drift from intervention protocol.

Health Coach Software Application: (see Appendix 1 for full size graphics and reports).

The health coach software application provides three types of reports. The overview report (Fig. 13) allows health coaches to succinctly ascertain the status of their participants and flag anyone who may be experiencing problems. The health coach may select a

participant from the overview to display the trend report (Fig. 14). The trend report allows the health coach to review the participant's progress between weekly health coaching sessions. Finally, the health coach may select a day from the trend report to display a detailed report (Fig. 15). These three reports are updated after the results of the pilot studies (preliminary data projects 1 and 3) are generated.

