Missing Values treatment: Initially, Little's test for missing completely at random (MCAR)³⁶ will be used along with Potthoff and colleagues assessment of missing at random (MAR+).³⁷ Contingent on either MCAR or MAR data, imputation will be considered in order to respond to the level of missing-ness and to be able to use the optimal amount of information in our model. In case of participant withdrawal, all available data will be used.

Path analysis: The hypothesized framework will be tested using structural equation modeling (SEM), which allows us to examine multiple dependent variables in one model and concurrently describe multiple paths of direct and indirect effects among the theoretical constructs. We will use two steps in SEM analyses. First, the validity of the measures will be assessed by fitting a measurement model and investigating whether the items are strong indicators of the latent constructs (e.g., self-efficacy and quality of life). The second step involves testing the effect of the predictor variables (e.g., MI training, mastery in PA, social persuasion, physiological and emotional states) on the outcome variables (e.g., self-efficacy, self-management, and physical QOL) with a particular interest in the role self-efficacy has in increasing self-management and physical QOL. In addition to the direct effects of MI training on self-efficacy, self-efficacy on self-management, self-management on physical QOL, mediating effects can be tested, such as the effects of MI training on self-management and physical QOL, or effects of self-efficacy on physical QOL by estimating their indirect effects. The model will be tested using lavaan, the R software package for SEM.³⁸ The model fit will be examined by its model χ^2 , goodness-of-fit index (GFI), and root mean square error of approximation (RMSEA).

Qualitative Analysis (Aim 4): Perceptions of the participants and the interventionist will be captured using qualitative methods. Qualitative inquiry in randomized controlled trials help interpret results and variation in results.³⁹ It can also help ensure that interventions meet stakeholder needs and therefore aid in future transferability of interventions like the proposed system. This is increasingly important as trials move out of controlled settings and into the social context of natural settings,⁴⁰ including participant homes.

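### The path analysis plans effects of MI training apart from exercise, but the trial delivers both only as one package, so the MI path is a coaching effect only under assumptions the plan does not state

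*Combined protocol and SAP*

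**What the plan says.** The Path analysis paragraph of the Analysis Plan describes a structural equation model whose second step is "testing the effect of the predictor variables (e.g., MI training, mastery in PA, social persuasion, physiological and emotional states", the outcomes being self-efficacy, self-management and physical quality of life. It continues: "In addition to the direct effects of MI training on self-efficacy, self-efficacy on self-management, self-management on physical QOL, mediating effects can be tested". The examples it gives of such mediating effects include those of MI training on self-management and on physical quality of life. Fit is to be judged by the model chi-square, GFI and RMSEA. The paragraph gives no assessment time for the model.

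The Theoretical Framework section separates the routes: PR acts on "mastery in PA, by engaging in daily exercises (Aim 3, measured by activity monitor), social persuasion (weekly feedback from a trustworthy coach", while MI training is described as something the coach receives. It then says "A proposed path analysis will confirm the proposed framework".

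On design, the Randomized Study section says "Participants will be randomly assigned in equal proportion to one of two treatments: home PR with health coaching or the attention waitlist control". Coaching calls run weekly over the 12 weeks of home PR. Under Attention Waitlist Control Group Procedure, controls receive the active intervention from month four, again as a package. The documents describe control contact before then in two ways (non-coaching calls, or a pamphlet and two letters); neither includes coaching or home PR.

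On MI data, all calls are recorded and "10% of all calls will be reviewed", for feedback and training of the coaches. No fidelity or dose score is named as an input to the model.

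**The concern.** A model with MI training and activity as separate predictors invites the reader to take the first coefficient as what coaching does and the second as what exercise does. The trial randomises neither component on its own. The only documented variable that could stand for a participant's MI exposure is randomised arm, and arm also stands for the exercise video, the walks, the monitors and the tablet.

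What is at stake is attribution. One of the listed aims reads "The addition of formal SM support through health coaching during PR may promote behavioral change", which is a statement about the increment from coaching. A reported direct or indirect effect of MI training would look like evidence for that increment, and this design cannot supply it. The Analysis Plan calls its summaries out to nine months descriptive and exploratory but gives the path analysis no such label, and the Limitations paragraph does not mention the issue.

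**Working it through.** The plan gives no sample size, power or effect size for the path analysis, so there is no figure to reproduce. The check concerns what the MI path can mean. Inputs from the documents: 100 participants per arm (Sample Size), two arms, and a two-sided 5% level (Analysis Plan). All effect sizes below are assumptions.

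**1. Components as assigned.** Let C be coaching assigned and E be home exercise assigned. For all 200 participants C = E = arm. The matrix [intercept, C, E] has rank 2 of 3 and the correlation of C with E is 1.00. Assignment alone therefore identifies only the sum of the two effects.

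**2. Controls who obtain centre-based PR.** The Limitations paragraph expects some but gives no share; 5%, 10% and 20% of controls are assumed. Variance inflation for the coaching effect is 1/(1 − r²), where r is the correlation of coaching with any PR received:

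- 5%: 1/(1 − 0.9048) = 10.5
- 10%: 1/(1 − 0.8182) = 5.5
- 20%: 1/(1 − 0.6667) = 3.0

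The matrix now has full rank, but the separation rests on 5 to 20 controls who were not randomised to PR and who received a different kind of PR.

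**3. The model nearer to the plan, with measured activity.** Let A be arm, M activity and Y self-efficacy:

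- M = 0.5A + u
- Y = cA + eA + 0.3M + v

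Here u and v are standard normal, c is the coaching effect, and e is the exercise effect that does not pass through measured activity. Regressing Y on A and M, the coefficient on A is c + e. The total arm effect is c + e + 0.3 × 0.5 = c + e + 0.15.

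**4. Measurement error in activity.** With reliability 0.5, the slope on observed activity is 0.3 × √0.5 = 0.212 and the arm shift in it is 0.5 × √0.5 = 0.354. The part attributed to activity is 0.212 × 0.354 = 0.075. If c = e = 0, the coefficient on A is 0.15 − 0.075 = 0.075 rather than 0.

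**5. Simulation**, 4,000 trials per row, 100 per arm:

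| c (coaching) | e (exercise not via monitor) | Reliability of activity | Coefficient labelled MI | Significant | Total arm effect |
|---|---|---|---|---|---|
| 0.4 | 0 | 1 | 0.40 | 78% | 0.55 |
| 0 | 0.4 | 1 | 0.40 | 78% | 0.55 |
| 0.2 | 0.2 | 1 | 0.40 | 78% | 0.55 |
| 0 | 0.2 | 1 | 0.20 | 28% | 0.35 |
| 0 | 0 | 1 | 0.00 | 5% | 0.15 |
| 0 | 0 | 0.5 | 0.08 | 8% | 0.15 |

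The first three rows cannot be told apart. The fifth shows when the MI label would be safe: all of the exercise effect passes through activity, measured without error. The simulation covers only the first equation of the model and includes no unmeasured confounder of mediator and outcome.

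**The case against.** The strongest reply is that the plan does not enter PR exposure beside MI. It enters mastery in physical activity, which the Theoretical Framework says is measured by activity monitor and which differs between individuals. That model can be fitted, and the fifth row of the table gives the right answer. This stands: the problem is interpretation under unstated assumptions, not failure of estimation. A reader might infer from the two-arm design that the MI coefficient cannot be estimated at all, or that coaching and PR received are perfectly correlated. Neither follows, because activity is not the same column as arm and some controls may receive centre-based PR.

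Other stronger readings are also unsupported:

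- **That the whole arm effect would be labelled MI.** In the first three rows the share is 0.40/0.55 = 73%, and the other listed predictors could take more.
- **That no MI data exist.** Calls are recorded and coach notes are kept in REDCap. What is missing is a measure named for this model.
- **That reversed arrows would fit equally well.** The plan describes a chain starting from MI training. If that first variable is randomised arm, reversing the later arrows changes the implied conditional independences. Equal fit would need direct arm paths that saturate the model, which the plan does not state.
- **That every variable is read at month 3.** Measures are taken at baseline, three, six and nine months; the model's timing is simply not given.
- **That the sponsor will use the result to support the coaching aim.** The documents do not say so. The aim is hedged, and Hypotheses 1 to 3 compare arms.

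**Conclusion.** The point holds as a matter of attribution. If MI training is represented by arm, its path is the effect of home PR plus coaching that does not pass through the measured mediators. It can be read as a coaching effect only if three things are true:

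- exercise acts solely through the measured mediators;
- those mediators are measured without error;
- no unmeasured factor affects both mediator and outcome.

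The plan states none of these. The third is open to doubt on the plan's own measures, since self-efficacy (CRQ Mastery) and physical quality of life (CRQ physical summary) come from one questionnaire. Centre-based PR among controls is not randomised and does not separate the components.

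The sizes shown (0.40 under three different causes; 28% significance with no coaching effect) depend on assumed effects. That arm cannot distinguish coaching from exercise outside the mediators follows from the design. Saying that the path analysis will confirm the framework is therefore too strong. The primary arm comparisons of Aims 1 to 3 are unaffected.

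**What to change.** - In the Path analysis paragraph, replace MI training with randomised arm, labelled *home PR plus coaching*.
- Specify month 3, the last assessment before controls receive the package, and regress each month-3 mediator and outcome on its own baseline value.
- State the three mediation assumptions and add a sensitivity analysis, for example over a range of mediator–outcome residual correlations and activity reliabilities.
- Label the mediated paths exploratory and report none as an effect of MI coaching alone.
- In the Theoretical Framework section, say that the path analysis will explore the framework rather than confirm it.
- If coaching dose or call fidelity is analysed, label it observational and within-arm.

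The cost is a text change in protocol and analysis plan plus modest extra programming, with the same data and software. Baseline adjustment alone does not remove confounding or measurement error, which is why the sensitivity analysis is needed. The downside is a narrower claim about coaching.

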“Very helpful. Very visual. Tablet was portable which allows people who need visual training to follow along.”
“Wasn’t that difficult, could see where if someone would stick with it they would benefit.”

Were there things you didn’t like?

“I mentioned to the day that you showed me this that the slow walking bothered to me, but then when you explained to me that the slow walking really helps me work on my balance, I really thought about it and plan to really work on it.”

Is there anything we could do differently or that we need to change?

“I think the human component is very important, to feel that someone is checking up. It would be nice to have variation in the exercises. I don’t think I could do the same exercises for 8 weeks. I really liked the pursed lipped breathing exercise.”

Fig. 8. Qualitative pilot feedback of the home pulmonary rehabilitation program.

Study Design and Methods

Methods: *Describe, in detail, the research activities that will be conducted under this protocol:*

Pilot Study: When the technology is ready, we will conduct a pilot study enrolling fifteen or fewer participants. The participants in the pilot study will not be randomized and will receive the Intervention. The purpose of the pilot study is to observe how the technology works in real life and to refine the intervention if needed. The participants in the pilot study will complete all measures and activities of the randomized control trial, minus the randomization.

Characteristic	Control	Intervention	NNT	P Value
CRQ Emotional Function				
Δ6 Month – Baseline, mean (SD)	0.10 (1.0)	0.50 (1.0)		0.004
Δ12 Month – Baseline, mean (SD)	0.15 (0.9)	0.43 (1.0)		0.058
% improved >MCID at 6 months	14.1	29.9	6	0.018
% improved >MCID at 12 months	14.3	28.8	6	0.036
CRQ Physical Function				
Δ6 Month – Baseline, mean (SD)	-0.01 (1.0)	0.33 (0.9)		0.036
Δ12 Month – Baseline, mean (SD)	-0.04 (1.0)	0.27 (1.0)		0.016
% improved >MCID at 6 months	12.8	26.0	7	0.038
% improved >MCID at 12 months	11.4	19.2		0.199
ΔPhysical Activity Level at month 6	0.01	0.01		NS
ΔPhysical Activity Level at month 12	0.01	-0.10		NS
Died in First 12 Months, n (%)	12 (11.3%)	10 (9.3%)		0.620

NNT, Number Needed to Treat ; MCID, Minimal Clinically Important Difference

Fig. 6. Quality of life outcomes from health coaching

Qualitative Interviews	N=24
Confidence in taking care of health (mean ± SD)	8.05 ± 1.99
Helpfulness of the intervention (mean ± SD)	9.60 ± 0.60
Frequency of calls (%)	
Too little	22%

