Data will be stored in Mayo Clinic's REDCap database. Mayo Clinic Florida and Health Partners will only be able to see data from their site. Mayo Clinic Rochester will have access to data entered into REDCap as they are the coordinating site for this trial. REDCap (Research Electronic Data Capture) is a secure, web-based application designed to support data capture for research studies, providing: 1) an intuitive interface for validated data entry; 2) audit trails for tracking data manipulation and export procedures; 3) automated export procedures for seamless data downloads to common statistical packages; and 4) procedures for importing data from external sources.

Health Coaches located at Mayo Clinic Rochester may fill in as Health Coaches at other sites to cover vacations, absences and employment gaps in health coaches. Mayo Clinic Rochester Health Coaches only have access to data in REDCap (demographics and health coach notes) and not the medical record.

Data Analysis and Data Safety Monitoring

DSMB

See Data Safety Monitoring Charter.

Analysis Plan

Page 11 of 17

There are three *distinct* quantitative study hypotheses (inform different aspects of the process). Hypothesis 1 (Aim 1) states that participants on home-based PR will have higher physical (dyspnea fatigue) QOL at month three than participants in the waitlist control group as measured by the CRQ physical summary score. Hypothesis 2 (Aim 2) is that participants on home-based PR will have better SM abilities at month three than participants in the waitlist control group. The SMAS-30 will be used to test this hypothesis. Hypothesis 3 (Aim 3) is that participants on home-based PR will have more daily PA than participants in the control group at month three. This will be measured by steps and minutes spent in sedentary, light, and moderate activity measured by the ActiGraph^{34,35} and greater self-efficacy for exercise. This study has two activity monitors, the ActiGraph, a gold standard activity monitor used for outcome measures (7-day wearing) at baseline, 3, 6 and 9 months. The Garmin Vivofit PR activity monitor used daily during PR period will NOT be used as an outcome measure, just for health coaching and participant awareness of physical activity (participant will keep this activity monitor after PR).

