For the continuous study outcomes, changes from baseline to three months will be compared between the study arms using two-sample, two-sided t-tests with 5% type I error rates. Changes in QOL and number of steps will be compared between the two treatment sequences using two-sample two-sided t-tests. No adjustments will be made for multiple testing. Means, SDs, medians, ranges, and frequency distributions will be reported and plotted over time by study arm. Additional analyses will compare changes from baseline to three months. Linear models will be used to assess the impact of treatment arm on three month outcomes after adjusting for the corresponding baseline measure and other variables related to the outcome (age, degree of breathlessness at baseline using the mMRC, and FEV1). Repeated measures mixed models will be used to estimate the intervention effect over the three months of the comparison study. Although there is a crossover element to the study design, crossover analyses will not be used due to the anticipated carryover effect in the intervention arm. Intent-to-treat analyses will also be performed to determine the sensitivity of the results to dropouts and missing values. In the intent-to-treat analyses, if a month three measure is missing for any reason, it will be described as not changing from baseline. Health care utilization (number of ED visits, hospitalizations, and length of stay) between baseline and three months will be treated (analyzed) as both binary (for incidence rates) and continuous (for the number of events). The binary endpoints will all be compared between groups using Fisher's exact test. Logistic regression models will also be fit to look for differences in these outcomes by arm after adjusting for age, mMRC, FEV1, baseline levels of anxiety, depression, and fear, and baseline health care utilization (before starting the study). While significant missing-ness (>5%) in the Aim 1 outcome is not expected, imputation is planned in case it is.

Descriptive summaries of the changes between baseline, three, six, and nine months will be used to assess the effect of the delayed intervention on the control arm and the residual beneficial effect on the intervention arm. These results will be only descriptive and exploratory. No formal hypothesis testing will be done. All data will be stored in REDCap and analyzed using SAS (Cary, NC).

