Integration with Aims 1-3: The function of the mixed-methods design is elaboration of the quantitative data on effectiveness with the qualitative findings. After initial quantitative and qualitative analyses are complete, the investigators will place findings side-by-side to explore connections as well as divergent findings that need further exploration. This includes within- and between-case analysis to understand the perspectives of participants who differed on comparative effectiveness outcomes (Aim 1-3) as well as those who differed in important baseline characteristics such as participant activation.

Sample Size: We will enroll a total of 200 participants, with 100 in each arm. Sample size calculations are based on two-sample, two-sized t-tests comparing the two groups at 3 months. **Aim 1:** We calculated the sample size based on estimates from our previously published data⁶. From this research, the CRQ has a SD of about 1.13. A total sample of 189 participants (94 or 95 per group) is needed to detect a difference of 0.5 (the minimal clinically important difference) in the CRQ with 80% power. Based on our previous health coaching application (R01HL09468 [name], PI),⁶ we expect 5% attrition. We will therefore enroll 200 participants, 100 in each arm.

Aim 2: A sample size of 128 is needed to detect a half SD change in SMAS-30 based on COPD studies using this measure. **Aim 3:** The number of steps recorded by the AM is considered a valid measure of PA in patients with COPD and the elderly. The clinically meaningful difference in steps is estimated at 1100. Therefore, a sample size of 170 participants (85 per group) is needed considering a SD of 2500 steps from our previous study.⁶ **Aim 4:** The sample size of 40 completed participant interviews is within standards for qualitative research, but interviewing and analysis will take place concurrently and iteratively to inform the sampling plan. We will continue interviewing until saturation (the point at which interviews are not yielding much new information) is reached; the sample

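### The Aim 1 sample size of 189 for 80% power does not follow from its stated inputs, which give about 164, and the plan does not say whether its SD belongs to the change score that will be tested

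*Combined protocol and SAP*

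**What the plan says.** Under Sample Size, the protocol describes the basis for all aims in one sentence: "Sample size calculations are based on two-sample, two-sized t-tests comparing the two groups at 3 months". For Aim 1 it draws on the sponsor's earlier published work: "From this research, the CRQ has a SD of about 1.13". With a difference of 0.5, taken as the minimal clinically important difference, and 80% power, it states a total of 189 (94 or 95 per group). It then allows for 5% attrition and arrives at 200, 100 per arm.

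Under Analysis Plan, Hypothesis 1 is worded as a level: "participants on home-based PR will have higher physical (dyspnea fatigue) QOL at month three", measured by the CRQ physical summary score. The planned test is on change: "changes from baseline to three months will be compared between the study arms using two-sample, two-sided t-tests with 5% type I error rates". The same section says "No adjustments will be made for multiple testing", so the 5% level applies to Aim 1 in full. Linear models for the three-month outcome, adjusted for its baseline value, are listed as additional analyses.

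Fig. 6 (Preliminary Data, Project 2) gives the SD of change in CRQ Physical Function in the sponsor's health coaching trial: 1.0 (control) and 0.9 (intervention) at month 6, and 1.0 in both arms at month 12. No SD of change at month three is given.

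**The concern.** There are two separate problems in one short paragraph.

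The first is arithmetic. The inputs printed next to 189 do not produce it. Either the figure is wrong or it rests on an input that is not printed. This is so whatever 1.13 measures.

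The second is the link to the analysis. The test compares changes, so the SD that matters is that of the month-three change in the physical summary score. The paragraph gives one SD for the CRQ without saying whether it is for a score or a change, or for which CRQ scale. The change SDs shown elsewhere in the plan are smaller.

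At stake is what the trial can claim about its own sensitivity. A reader who takes 80% at face value cannot tell how much power the planned test has, or how much missing data it can absorb beyond the 5% allowed for.

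**Working it through.** **Inputs.** Difference 0.5, SD 1.13, power 80%, stated N 189, attrition 5% (Sample Size). Two-sided t-test on change, alpha 0.05, no multiplicity adjustment (Analysis Plan). Equal allocation (Randomized Study). Change SDs 0.9 to 1.0 (Fig. 6).

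**Step 1: reproduce 189.** The normal approximation is n per arm = 2 × SD² × (1.960 + 0.842)² / difference².

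- 2 × 1.13² × 7.849 / 0.25 = 80.2, so 81 per arm and 162 in total.
- The exact noncentral-t solution is 81.1, so 82 per arm and 164 in total.

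The stated 189 is 25 higher than the exact figure. Attrition does not explain the gap: 164 / 0.95 = 173. The 5% is in any case applied after 189, since 189 / 0.95 = 199, which fits the 200 enrolled.

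**Step 2: what would give 189?**

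- One-sided 80% power gives 128; two-sided 90% power gives 216 by the normal approximation. Neither fits.
- Two-sided 85% power gives 184 (exact t, 186). This is close, but the text says 80%.
- Dividing 164 by a Wilcoxon efficiency of 0.864 gives 190, but the text names t-tests.
- With 189 and 80% power held fixed, the SD must be about 1.22, or the difference about 0.46 at SD 1.13.

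At SD 1.13, 94.5 per arm gives 86% power.

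**Step 3: the planned test.** After 5% attrition, 200 enrolled leaves 190, or 95 per arm. Exact-t results for a 0.5 difference in change:

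| SD of month-three change | Total N for 80% | Power at 95 per arm |
|---|---|---|
| 0.9 (Fig. 6, low) | 104 | 97% |
| 1.0 (Fig. 6, high) | 128 | 93% |
| 1.13 (if it is already a change SD) | 164 | 86% |
| 1.24 (see step 4) | 196 | 79% |

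**Step 4: if 1.13 is the SD of a score.** With equal SDs at both visits and correlation r between baseline and month three, SD of change = 1.13 × √(2(1 − r)).

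- r = 0.5: 1.13 × √1.0 = 1.13.
- r = 0.4: 1.13 × √1.2 = 1.24.
- For a change SD of 1.0: r = 1 − 1.0² / (2 × 1.13²) = 0.61.
- For a change SD of 0.9: r = 1 − 0.9² / (2 × 1.13²) = 0.68.

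The plan gives no correlation, so these values only show the range.

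**Step 5: separate the two effects.** At 95 per arm, the move from the stated 80% to 86% is the arithmetic discrepancy. The further move from 86% to 93–97% comes only from replacing 1.13 by the Fig. 6 SDs.

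**The case against.** The strongest reply is that nothing harmful follows. On the plan's own SD the trial has more power than it claims, and at the Fig. 6 SDs more again. Planning with a larger SD than the analysis may meet is a legitimate, cautious choice. A month-three comparison is also not foreign to the plan: Hypothesis 1 is worded that way, and baseline-adjusted models of the three-month outcome are planned. All of this stands, and it is why the point is minor. It does not make 189 reproducible. The reassurance about power also depends on the SD of change, which the plan leaves unstated.

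Three stronger readings are tempting, and the documents do not support them.

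- **That the whole gap comes from sizing a level and testing a change.** It does not: 189 already fails against SD 1.13 before any change score enters.
- **That 1.13 is known to be the SD of a single-visit score.** That is a natural reading of "the CRQ has a SD of about 1.13", but the plan does not label it. The correlations in step 4 depend on that reading.
- **That the trial certainly has 93% to 97% power.** Those figures carry SDs from months 6 and 12 of a trial without home rehabilitation over to month three. The SDs are also rounded to one decimal: a printed 1.0 covers 0.95 to 1.05, which is 116 to 142 participants for 80% power.

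Nor can a reader infer that the trial is underpowered. Of the SDs examined, only 1.24 takes power below 80%, and then by about one percentage point.

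**Conclusion.** The point holds in a limited form. As written, 189 for 80% power is not what a two-sided 5% t-test gives for a difference of 0.5 and SD 1.13: the answer is about 164, and 189 gives about 86%. It also does not describe the planned change-score test at the only physical change SDs in the plan, where 104 to 128 would suffice for 80%.

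The arithmetic finding rests only on the stated inputs. The second finding is that the basis of the SD is undocumented; a level-versus-change mismatch is plausible but not proven. Power at 95 per arm lies between about 79% and 97% for change SDs from 1.24 down to 0.9, and the error is conservative if the month-three SD is near Fig. 6. No planned analysis or enrolment target has to change, so this is a correction of reporting and not a threat to the trial's validity.

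**What to change.** Rewrite the Aim 1 sample size paragraph and keep 200 enrolled.

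1. Correct 189, or state the input that produces it (for example a different power, SD or test).
2. Say what 1.13 measures: score or change, which CRQ scale and which visit.
3. State the assumed SD of the month-three change in the CRQ physical summary score, or the score SD together with the baseline correlation. If Fig. 6 is used, say that its SDs are from months 6 and 12 of a coaching-only trial and that applying them at month three is an assumption.
4. Restate power for the change-score t-test at 95 per arm over a range of SDs, as in the table above.
5. Present any missing-data scenario beyond the stated 5% attrition as an illustration only.

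The cost is one paragraph of text. Items 1 and 2 need the sponsor to look up how the original calculation was done. Enrolment and the planned tests do not change.
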